Specific Aim 2: Aim 2 will investigate factors associated with implementation and effectiveness outcomes across the 10 clinic sites. This aim is guided by the Consolidated Framework for Implementation Research (CFIR), using implementation constructs and outcomes recommended by Proctor et al. Sources of data for this aim will include process records as well as quantitative and qualitative data from PNs; clinic administrators, staff, and providers; and parent participants. Consistent with CFIR, we will assess PN knowledge and behaviors following completion of the PN curriculum, including intervention fidelity; PN characteristics; inner and outer setting clinic characteristics; and four key implementation outcomes: adoption, recruitment/retention, reach/penetration, and sustainability.

Specific Aim 3: Aim 3 involves incremental cost-effectiveness analyses in which net costs and net effectiveness of the intervention will be compared with that of standard of care for patients referred to OCSHCN clinics after a failed newborn hearing screen. Hypothesis: (a) PN after a failed newborn hearing screen will be cost effective compared to the standard of care from the perspective of third-party payers. We will compare net costs and effectiveness of PN compared to standard of care. Results will be expressed as a ratio of differences in observed costs to differences of observed outcomes. The perspective of this evaluation will be third party payers.

Study Design

Describe and explain the study design (e.g., observational, secondary analysis, single/double blind, parallel, crossover, deception, etc.).

- *Clinical Research:* Indicate whether subjects will be randomized and whether subjects will receive any placebo.
- *Community-Based Participatory Research:* If you are conducting [community-based participatory research \(CBPR\)](#), describe strategies for involvement of community members in the design and implementation of the study, and dissemination of results from the study.
- *Qualitative research:* Indicate ranges where flexibility is needed, if a fixed interview transcript is not available, describe interview topics including the most sensitive potential questions.

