Patient Navigators: Baseline data collection from PNs will occur immediately following study enrollment and before PN training, administered by a trained interviewer. At the conclusion of PN training, PNs will take an examination to ensure comprehension of critical principles necessary for successful navigation. A score >80% will be required to pass the training. PNs with less than a passing score will be allowed to repeat relevant training elements and retake the examination one time; if the examination is not passed on the second round, the PN will no longer be employed in this study and a new PN will be identified. For those who pass the examination and proceed to intervention delivery, PNs will (1) audio-record 10% of PN sessions (with parent permission) to allow assessment of fidelity, (2) complete a PN fidelity checklist following each PN session (6 total checklists), and (3) maintain process logs detailing time, travel, attendance, frequency and modes of contact with families, and other activities and expenses associated with PN delivery.

Approximately 6 months after completing PN training, PNs will complete post-test assessments and key informant interviews, administered by a trained interviewer. PNs will be compensated \$25 at baseline and post-test for completing the battery of assessments. In each clinic, PN will continue after the 6-month assessment time point until the end of the 2nd quarter of Y5. These data will be shared with the CAB quarterly and recommendations on additional PN training or PN modifications will be observed.

Clinic Administrators, Staff, and Providers: Approximately 6 months after crossing to the PN condition, administrators, staff, and providers from each clinic will participate in key informant interviews and complete quantitative measures administered by a trained interviewer.

Parent Participants: At the Aim 1 post-test assessment (16 weeks post-birth), parents will complete a PN satisfaction measure and questionnaires. Selected parents (N~40) will also complete a 1-hour semi-structured key informant interview exploring parents' experiences with the PN intervention.

For Specific Aim 3:

Both direct and indirect costs associated with PN will be included. Costs associated with the initial newborn hearing screen will be excluded from analyses since these costs are incurred for all infants regardless of outcomes.

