Direct costs include the cost of: PN establishment (PN recruitment and training costs), program implementation (office space, PN time, PN travel and tools, PN materials, PN supervision, staff turnover), parent time and travel (travel to seek diagnostic or PN services, time

spent receiving diagnostic services), treatment costs (costs of a rescreen or diagnostic audiology appointment), nonmedical costs (potential cost savings due to earlier identification), and non-adherence costs for the clinics (no-show appointments). Research activity costs (e.g., data collection, human subject protection training of PNs) are not included.

Indirect costs include opportunity costs of time (e.g. loss of productivity/wages) for the parent(s).

Effectiveness: The measured outcome of effectiveness to which costs will be compared is the proportion of individuals in each group who achieve diagnosis by 3 months of age. We will derive these outcome data using clinic-level non-adherence rates reported monthly by EHDI, collected in Aim 1.

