Costs: Both direct and indirect costs associated with PN will be included. Costs associated with the initial newborn hearing screen will be excluded from analyses since these costs are incurred for all infants regardless of outcomes. Direct costs include the cost of: PN establishment (PN recruitment and training costs), program implementation (office space, PN time, PN travel and tools, PN materials, PN supervision, staff turnover), parent time and travel (travel to seek diagnostic or PN services, time spent receiving diagnostic services), treatment costs (costs of a rescreen or diagnostic audiology appointment), nonmedical costs (potential cost savings due to earlier identification), and non-adherence costs for the clinics (no-show appointments). Research activity costs (e.g., data collection, human subject protection training of PNs) are not included. Indirect costs include opportunity costs of time (e.g. loss of productivity/wages) for the parent(s). Cost data will be collected and monitored annually throughout the study period, for both the intervention and standard of care conditions. Unit program costs will be documented as Aims 1 and 2 are implemented and sustained over the study period. Unit costs of PN and parent participant travel will be estimated using the distance between patient and clinic address/zip code multiplied by the standard GSA standard mileage rate and adding any lodging expenses (if applicable). Unit costs of PN time and PN supervision will be estimated using logs maintained by the PNs and supervisors, applying the hourly PN pay rate (or related rate for supervisor). Parent participant time will be estimated using the average wage rate for Kentucky (estimated using average wage data from the Bureau of Labor Statistics (BLS)). Unit treatment costs will be estimated using administrative charge data from the OCSHCN, aggregated at the clinic level. Unit cost savings associated with early identification will be estimated using data from the literature. Unit costs of non-adherence will be based on costs of PN time not used but spent (which may vary if services are centralized versus local) and staff costs associated with rescheduling as documented in staff logs. Loss of productivity will be estimated using an estimate of time away from work (calculated using driving distance) and lost wages for one parent, using BLS average wage statistics. Where cost related data are tied directly to PN reporting/logs, data will be reviewed and checked monthly to ensure consistency and check validity.

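### Aim 3 declares a third-party-payer perspective, but its cost rule includes and values two family-borne categories, with no payer-only subset or second perspective in the visible text

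*Combined protocol and SAP*

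**What the plan says.** Under Objectives, Specific Aim 3, the perspective is stated twice. The hypothesis reads "PN after a failed newborn hearing screen will be cost effective compared to the standard of care from the perspective of third-party payers", and the paragraph closes with "The perspective of this evaluation will be third party payers". The form of the result is also fixed there: "Results will be expressed as a ratio of differences in observed costs to differences of observed outcomes".

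Under Study Design, For Specific Aim 3, the inclusion rule is "Both direct and indirect costs associated with PN will be included". Parent time and travel appears in the list of direct costs. The opportunity cost of parents' time, including lost productivity or wages, is the indirect cost. Research Procedures, Specific Aim 3, repeats the list and adds valuation rules. Travel is distance multiplied by a standard mileage rate, plus any lodging. For time, "Parent participant time will be estimated using the average wage rate for Kentucky". For the indirect cost, "Loss of productivity will be estimated using an estimate of time away from work (calculated using driving distance) and lost wages for one parent".

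Both sections state two exclusions only: the initial newborn hearing screen and research activity costs.

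**The concern.** The perspective of an economic evaluation decides which costs belong in the numerator. A third-party payer does not bear a parent's mileage, hours or lost wages. An analyst who follows the cost rule will include those costs, and one who follows the perspective statement will leave them out. The two give different ratios from the same data, and the plan does not say which one tests the hypothesis.

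The stake is the interpretation of Aim 3. If the listed costs are pooled, the result answers a broader question than whether navigation is cost-effective for payers.

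**Working it through.** The documents state no Aim 3 figure (no unit cost, ratio or threshold), so there is nothing to reproduce. The check is a comparison of the text, followed by the algebra of the ratio.

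**Step 1. Perspective against cost list.**

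| Element | Where | What it says |
|---|---|---|
| Perspective | Objectives, Aim 3 (twice) | Third-party payers |
| Result | Objectives, Aim 3 | Cost difference over outcome difference |
| Inclusion rule | Study Design; Research Procedures | Direct and indirect costs both enter |
| Family category 1 | Same, direct costs | Parent time and travel |
| Family category 2 | Same, indirect costs | Parents' lost productivity or wages |
| Exclusions | Same | Newborn screen; research activity |
| Payer-only subset | Aim 3 text in all three sections | None found |
| Second perspective | Aim 3 text in all three sections | None found |

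**Step 2. Are the family items only collected, or counted?** The inclusion rule is followed at once by a statement that newborn-screen costs are left out of the analyses, so inclusion is most naturally read as inclusion in the analyses. Each family item also has its own valuation rule. The plan states exclusions where it wants them, and these items are not among them.

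**Step 3. Effect on the ratio.** Let F be the net family cost per infant (navigation minus standard of care), R the net cost per infant from all other listed lines, and dE the difference in the proportion diagnosed by 3 months.

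- Ratio from the list as written: (R + F) / dE
- Ratio with the two family categories removed: R / dE
- Difference: F / dE

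F cannot be obtained. Research Procedures names sources (a mileage rate, average wages, clinic charges, navigator pay, the literature) but gives no dollar value for any of them. The sign of F is unknown too.

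As illustration only, the Background reports non-adherence of 38% under standard of care and 7% with navigation in the earlier academic-setting trial. Taking dE = 0.38 - 0.07 = 0.31, each net $1 of family cost per infant moves the ratio by 1 / 0.31 = $3.23 per additional timely diagnosis. If dE were 0.20 or 0.10 (assumed values), the shift would be 1 / 0.20 = $5 or 1 / 0.10 = $10.

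**Step 4. Overlap within the family items.** Parents' time is priced at an average wage under direct costs. Parents' time away from work is priced at an average wage again under lost productivity. The text does not say that the two lines cover different hours, so F itself may count some hours twice.

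**The case against.** The strongest reply is that this is an ethics application that summarises a fuller source. Objectives and Study Design both point to the grant application, which is not reproduced. The Aim 3 hypothesis is labelled (a) with no (b), and the aim speaks of analyses in the plural. Research Sites assigns the cost-effectiveness aim to a second university under a separate contract. A payer subset or a second perspective may be set out in one of those places. Because the visible Aim 3 text is sparse throughout, its silence on a subset is weak evidence that none exists.

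That stands as a limit: the point concerns the visible plan, and the grant may resolve it. It does not remove the contradiction, which lies between two positive statements and not in a silence. The closing perspective sentence is also singular and covers the whole evaluation, not hypothesis (a) alone.

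A second reply is that the costs are itemised, so a payer subset can be extracted without new data. That is true and makes the repair cheap. It does not tell the analyst which ratio is the planned one.

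**Conclusion.** The declared perspective and the cost rule disagree on two categories: parent time and travel, and parents' lost productivity or wages. Followed as written, the plan does not produce the payer ratio named in its own hypothesis. The conclusion assumes only that families, not payers, bear parents' travel, time and lost wages, which is how the plan describes those items. No dollar size or direction can be given. The Aim 1 outcome and its test do not depend on this.

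A reader might infer more, but the documents do not support the following:

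- **That clinic no-show costs and literature-based savings are two further violations.** The plan attributes no-show costs to the clinics. An argument from the navigators' university employment would apply equally to all navigator programme costs. The plan needs to say whether these lines are in or out; it does not show them to be misplaced.
- **That navigator hours are counted twice.** Nothing shows the logged hours and the unused hours being added together.
- **That valuing treatment at clinic charges is an error, or that a specific payer must be named.** The source of the charges is stated openly and a class of payers is given. Both are matters for reporting.
- **That the payer subset would be chosen after enrolment closed.** The application records that enrolment ended. It does not show that the choice was still open then.

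**What to change.** 1. Make the base-case ratio payer-perspective by leaving out parent time and travel and parents' lost productivity. State explicitly that navigator programme costs (establishment, time, travel, supervision) are in it as the cost of the intervention. State whether clinic no-show costs and literature-based nonmedical savings are in or out.
2. Report the full cost list as a separately labelled societal analysis from the same data, with a rule that parent time is counted once across the direct and lost-productivity lines.
3. If the perspective is instead restated as societal, change the hypothesis to match and label this as a change to the plan.
4. If the grant application already defines a payer subset or a second perspective, carry that text into this plan.

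The cost is some rewording and one extra column of results. No new data are needed, because the lines are already itemised. A payer base case leaves family burden out of view, which is why the societal result should sit beside it.

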All aspects of the proposed research involve minimal risk. We will obtain self-reported data via phone interviews and quantitative paper-based questionnaires, and we will conduct key informant interviews. Patient navigation will involve phone contact between a parent and a navigator to assist in facilitating timely diagnostic care. All study personnel (i.e., investigators, collaborators, and navigators) will be trained in the protection of human subjects, and all data collection and management procedures have been designed to minimize the risk of a confidentiality breach.

Description of potential adverse events:

Possible adverse events (AE) include:

- Distress from answering questions about child hearing problems
- Required breach of confidentiality due to domestic violence and/or child abuse reporting laws

Any AE will be immediately reported to the PI, the IRB, and NIH. Referrals for professional services (e.g., counseling) will be provided to any impacted participants. Local referral lists for counseling services will be developed for each community, and Co-Investigator [name], who worked for nearly a decade as a licensed clinical social worker (LCSW) will facilitate these referrals.

Description of safety monitoring:

The study will involve 1120 parent-infant dyads, 30 patient navigators, and 30 clinic administrators, staff members, or hearing healthcare providers. We will conduct no medically intrusive screenings or interventions.

Appropriate measures and care will be taken in the recruitment of research participants from vulnerable populations. According to Kentucky state law, in the recruitment of parent participants under 18 years of age and their infant children, the participant may give consent for services for her/his child and herself/himself without the consent of the participant's parent or legal representative. This applies to research of minimal risk. We will also recruit infants who are wards of the state with the following special precautions. According to Kentucky state law, wards of the state will be recruited by identifying an advocate for the infant in addition to any other individual acting on behalf of the child as guardian or *in loco parentis*. This advocate will be an individual who has a background and

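### In any Aim 3 result that includes parent costs, parent time on navigator calls goes uncosted, which understates the incremental cost of patient navigation; the declared payer perspective is unaffected but conflicts with the cost list

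*Combined protocol and SAP*

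**What the plan says.** The cost list appears twice in the combined protocol and SAP, under Study Design (Specific Aim 3) and under Research Procedures (Specific Aim 3, Costs). In both places the parent item opens with "parent time and travel (travel to seek diagnostic or PN services", and in full it reads "parent time and travel (travel to seek diagnostic or PN services, time spent receiving diagnostic services". Travel is counted for diagnostic visits and for PN; time is counted for diagnostic services alone.

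A separate indirect item is broader: "Indirect costs include opportunity costs of time (e.g. loss of productivity/wages) for the parent(s", with nothing that limits it to diagnostic visits. Research Procedures then gives the measurement rules. Parent hours are priced: "Parent participant time will be estimated using the average wage rate for Kentucky". Lost work time is measured this way: "Loss of productivity will be estimated using an estimate of time away from work (calculated using driving distance) and lost wages for one parent". No other rule says how parent hours are to be obtained. The navigator's own time is costed from logs at the navigator pay rate.

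On delivery, Data and Safety Monitoring says: "Patient navigation will involve phone contact between a parent and a navigator to assist in facilitating timely diagnostic care". On records, the Aim 2 text for navigators has them "maintain process logs detailing time, travel, attendance, frequency and modes of contact with families".

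On perspective, the Objectives (Specific Aim 3) frame the hypothesis from the viewpoint of third-party payers and then state: "The perspective of this evaluation will be third party payers".

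**The concern.** PN is named for parent travel and not for parent time. For an intervention given by phone, call time is the burden that falls on parents by design. The navigator's minutes on a call are costed, while the parent's minutes on the same call are not.

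Standard of care has no navigator calls. The omission therefore does not cancel between conditions: it lowers the cost of PN only, and it passes in full into the PN-minus-standard-of-care difference. Where parent costs are included, that favours the Aim 3 hypothesis that PN is cost effective.

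**Working it through.** The plan states no Aim 3 cost, cost-effectiveness ratio or sample size, so it has no figure to reproduce. The check is a reading of the text, followed by an illustration of size.

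**Step 1: does any line capture call time?**

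- Direct parent item: travel for diagnostic or PN services, time for diagnostic services. Call time is not named.
- Indirect item: parents' opportunity cost of time. Call time would fit under it by name.
- Measurement of the indirect item: time away from work derived from driving distance. A phone call has no driving distance, so it contributes zero.
- Wage sentence: sets the price of a parent hour, not which hours count.

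A category broad enough to hold call time exists, but no stated method gives it a value above zero.

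**Step 2: direction under each perspective.**

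- Results that include parent costs: omitted cost under standard of care = 0; omitted cost under PN = calls × hours per call × wage, which exceeds 0. The incremental cost is understated.
- Payer perspective: parent time is outside the cost boundary in both conditions. Bias = 0.

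**Step 3: illustration of size.**

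Inputs from the documents: 1120 enrolled dyads, 66% of about 1700 referrals (0.66 × 1700 = 1122, which agrees with 1120); non-adherence of 7% with PN against 38% with standard of care in the earlier academic-setting trial (Background), a difference of 31 points.

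Assumed inputs, not in the documents: 10 to 30 minutes per call; $15 to $30 per hour; 3 to 6 calls per family. The upper number of calls reads the six fidelity checklists in Study Design as six sessions per family.

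Omitted cost per enrolled family = calls × minutes / 60 × wage:

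- Low: 3 × 10/60 × $15 = $7.50
- High: 6 × 30/60 × $30 = $90

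Over all enrolled families:

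- 1120 × $7.50 = $8,400
- 1120 × $90 = $100,800

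Per extra infant diagnosed by 3 months = cost per family / risk difference:

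- At 31 points: $7.50/0.31 = about $24; $90/0.31 = about $290
- At half that effect (15.5 points): about $48; about $581

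**The case against.** The strongest reply is the declared perspective. A reader might infer that Aim 3 as a whole will make PN look cheaper than it is. The documents do not support that without a condition: under a third-party-payer boundary parent time does not count, the bias is zero, and adding another parent-borne cost would move the analysis further from the perspective it declares. This stands, and the point is limited to results that include parent costs. It does not dispose of the point, because the cost list puts parent time, travel and lost wages into the analysis.

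Second, a reader might say that call time is excluded outright. The indirect item is general, and lost wages are given only as an example. This stands in part: the gap lies in measurement, and it shows only when that item is read with the driving-distance rule.

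Third, it is tempting to say that PN travel hardly occurs. Phone is the stated mode, but navigators also log travel and modes of contact, and the cost section prices PN and parent travel. No frequency of in-person contact is given, so that claim is not made here.

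Fourth, the size rests on assumptions. Call length and wage appear nowhere, and the six-checklist count appears in Study Design but not in the parallel Research Procedures text. A reader might also infer that the omitted parent time exceeds the extra parent time that is counted for diagnostic visits. That needs a visit length the documents do not give. It would also treat an infant not diagnosed by 3 months as a visit never made, when the visit may simply come later. The objection to any firm size stands.

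Finally, valuing short calls at the full average wage is a modelling choice. It is, however, the rate the plan already sets for parent time. The application also refers to an attached grant proposal, which was not available and may say more.

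**Conclusion.** The point holds in conditional form. In any Aim 3 result that includes parent costs, the cost list and measurement rules as written give parent time on navigator calls no value. That cost arises only under PN, so the incremental cost of PN is understated. The direction is certain; the size is not.

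The illustrative range of $7.50 to $90 per enrolled family depends wholly on the assumed number and length of calls and the assumed wage. The figures per extra timely diagnosis depend also on carrying over the earlier trial's effect. No total programme cost is given, so the weight of this item against navigator pay, training and supervision cannot be judged.

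Under the declared payer perspective the omission has no effect. The conflict between that perspective and a list containing parent costs is the wider fault, and it has to be settled first. Neither issue touches the Aim 1 primary outcome.

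**What to change.** 1. Reconcile the perspective in the Objectives with the cost lists in Study Design and Research Procedures. Report the payer-perspective result without parent time, travel or wages in either condition.
2. For every result that does include parent costs, extend the time element of the parent item, in both places, to cover PN contacts as well as diagnostic services, so that it matches the travel element.
3. State the measure: logged navigator contact minutes with the parent, multiplied by the Kentucky average wage rate already specified.

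The cost is a few words in two passages and one extra line in the cost model. The navigator logs already record time and frequency of contact, so no new data from families should be needed, and although enrollment has ended this can still be done at the analysis stage. The downside for the sponsor is a slightly less favourable PN figure in the results that include parent costs.
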